3.1.3 Double-blind Treatment Phase

The Double-blind Treatment Phase will continue in 28-day treatment cycles. The first dose of oral study treatment will be administered on Cycle 1 Day 1 and continue BID throughout the cycle as monotherapy; IV study drug will begin on Cycle 2 Day 1 (C2D1). Details on study drug administration are described in Section 5.5. During the Double-blind Treatment Phase, patients will come into the study site for a visit on Day 1 and Day 15 of Cycles 1 and 2, and on Day 1 of every cycle thereafter. Study treatment will continue until 24 months after initiating oral/IV combination study treatment, disease progression, or unacceptable toxicity, whichever happens first.

During the Double-blind Treatment Phase (continuous 28-day treatment cycles), patients will be monitored for safety and efficacy. Assessments will include AEs, physical examination, vital signs and weight measurement, central laboratory hematology, serum chemistry, and CA-125 measurement, concomitant medications, therapies and procedures, ECOG performance status, disease status assessment, ctDNA analysis, study drug administration and accountability, and PRO. ECGs and urinalysis will be performed as clinically indicated.

Blood samples will also be collected to determine whether any mutation identified is of germline or somatic origin and for PPK analyses.

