5.5.2 Nivolumab/IV Placebo

Nivolumab, or matching placebo, is administered IV as a 480 mg via a 30-minute IV infusion on Day 1 of every 28-day cycle, starting on Cycle 2. IV study drug infusion should be prepared as specified in the Pharmacy Manual. Refer to the current version of the IB and/or Pharmacy Manual for complete storage, handling, dispensing, and infusion information.

[figure not shown]

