5.6 Dose Modification Criteria

Doses of oral study drug, and/or IV study drug, may be interrupted or delayed for toxicity and other protocol specified criteria. Dose reductions are permitted for oral study drug but not for IV study drug. The assessment for delay or discontinuation should be made separately

for the oral study drug (rucaparib or placebo) and the IV study drug (nivolumab or placebo); however, if toxicity is considered related to all study drugs or if the investigator is unable to determine which study drug is the cause of the AE, then all study drugs in the combination should be delayed and/or discontinued. Dose delay criteria also apply for the placebo of each agent, given the blinded nature of this study. Treatment may be prematurely discontinued due to withdrawal of consent, unacceptable toxicity, disease progression, completion of treatment cycles, or termination of the study, whichever occurs first.

An integrated summary of dose modification guidance by CTCAE Grade v5.0 for events related to IV and/or oral drug is provided below in Figure 2. In addition to the guidance summarized, a dosing delay of > 14 days or > 8 weeks (2 or more consecutive cycles) with oral or IV drug, respectively, requires discontinuation except if approved by the study medical monitor/designee. More detail is provided in Section 5.6.1 (treatment delay and/or interruption), Section 5.6.2 (re-treatment criteria), Section 5.6.3 (dose reduction), and Section 5.6.4 (study drug discontinuation). Please also refer to Appendix 8: AE Criteria for Delay, Resume and Discontinue of Nivolumab.

Figure 2. Integrated Dose Modification Guidance for Events Related to IV and/ or Oral Drug by CTCAE Grade (CTCAE v5.0)

Abbreviations: AE = adverse event; ALT = alanine aminotransferase; AML = acute myeloid leukemia; AST = aspartate aminotransferase; BID = twice a day; CTCAE = Common Terminology Criteria for Adverse Events; DRESS = drug reaction with eosinophilia and systemic symptoms; IV = intravenous; MDS = myelodysplastic syndrome; SJS = Stevens-Johnson Syndrome; TEN = toxic epidermal necrolysis.

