Note: Rucaparib may cause transient AST and/or ALT elevations (without increased total bilirubin) at Cycle 1, Day 15 that begin to resolve by Day 29, even with continued rucaparib dosing.

Grade 2 or 3 colitis or diarrhea

- Grade 3 pancreatitis with symptoms. Grade 3 increased amylase or lipase without signs or symptoms of pancreatitis does not require dose delay
- Grade 2 rash covering > 30% body surface area or Grade 3 drug-related skin AE. Suspected Stevens-Johnson Syndrome (SJS), toxic epidermal necrolysis (TEN), or drug reaction with eosinophilia and systemic symptoms (DRESS)
- Endocrinopathies met the following criteria:
 - Grade 2 adrenal insufficiency.
 - Grade 2 or 3 hyperglycemia requiring initiation or change in daily management.
 - Grade 1-3 hypophysitis/hypopituitarism that is symptomatic and also associated with corresponding abnormal lab and/or pituitary scan.
 - Grade 2 or 3 hyperthyroidism or hypothyroidism.
- Grade 2 uveitis.
- Grade 2 neurological (other than Guillain-Barre Syndrome [GBS], myasthenia gravis [MG], encephalitis, or myelitis).
- Any grade of encephalitis or myelitis. After workup for differential diagnosis, (ie, infection, tumor-related), if it is not drug related, then dosing may resume when AE resolves.
- Myocarditis with symptoms induced from mild to moderate activity or exertion.
- Other Grade 3 drug-related AE with first occurrence lasting ≤ 7 days.
- Grade 3 drug-related laboratory abnormality (not listed above), with the following exceptions:
 - Grade 3 lymphopenia or Grade 3 increased amylase or lipase without signs or symptoms of pancreatitis does not require dose delay.
 - Grade 3 thrombocytopenia > 7 days or associated with bleeding requires for dose discontinuation.
 - AST, ALT, and/or total bilirubin elevations with a range of AST or ALT > 5 × ULN or total bilirubin > 3 × ULN, regardless of baseline value, will require dose delay or discontinuation. (See Section 5.6.4.2)*
- Any AE, laboratory abnormality, or intercurrent illness that, in the judgment of the investigator, warrants delaying the dose of study medication.

Participants who require dose hold should be re-evaluated weekly or more frequently if clinically indicated and resume dosing during the next scheduled dosing window (Cycle X, Day 1 ± 3 days) after re-treatment criteria are met (Section 5.6.2).

Please refer to Appendix 8: AE Criteria for Delay, Resume and Discontinue of Nivolumab.

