5.6.2.2 Nivolumab/IV Placebo

Participants may resume treatment with IV study drug when the drug-related AE(s) improve to Grade ≤ 1 or resolve to baseline value, with the following exceptions:

- Participants may resume treatment in the presence of Grade 2 fatigue and pancreatitis.
- Participants who are suspected with SJS, TEN, or DRESS may resume treatment if SJS, TEN, or DRESS are ruled out and rash reduces to < 10% body surface area.
- For participants with elevated AST, ALT, or total bilirubin elevations, dosing may resume when laboratory values return to baseline and management with corticosteroids, if needed, is complete.
- Drug-related pulmonary toxicity, diarrhea or colitis must have resolved to baseline before treatment is resumed. Participants with persistent Grade 1 pneumonitis after completion of a steroid taper over at least 1 month may be eligible for retreatment if discussed with and approved by the study medical monitor.
- Participants with Grade 2 uveitis may resume treatment if uveitis responds to topical therapy (eye drops) and after uveitis resolves to Grade ≤ 1 or baseline. If patient requires oral steroids for uveitis, then permanently discontinue study drug.
- For visual complaints, patients should be referred to an ophthalmologist following the guidance in Section 7.1.10 of the nivolumab Investigator's Brochure.

Participants with drug-related endocrinopathies adequately controlled with only physiologic hormone replacement may resume treatment after consultation with the study medical monitor.

Participants with Grade 2 neurological (other than GBS, MG, encephalitis, or myelitis) may resume when AE resolves to baseline

If the criteria to resume treatment are met, the patient should restart treatment at the next scheduled timepoint per protocol. However, if the treatment is withheld past the window period of the next scheduled timepoint per protocol to ensure adequate recovery from the adverse event or tapering of immunosuppression, the dosing should continue to be withheld until the subsequent scheduled timepoint.

If treatment is withheld > 8 weeks from the last dose (2 or more consecutive IV drug cycles missed), the subject must be permanently discontinued from study therapy, except as specified in Section 5.6.4.2.

Please refer to Appendix 8: AE Criteria for Delay, Resume and Discontinue of Nivolumab.

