- Any Grade 4 drug-related AE or laboratory abnormality (including but not limited to creatinine, AST, ALT, or total bilirubin), except for the following events that do not require discontinuation:
 - Grade 4 neutropenia ≤ 7 days
 - Grade 4 lymphopenia
 - Isolated Grade 4 electrolyte imbalances/abnormalities that are not associated with clinical sequelae and are corrected with supplementation/appropriate management within 72 hours of their onset
 - Grade 4 drug-related endocrinopathy AEs, such as, hyper- or hypothyroidism, or glucose intolerance and adrenal insufficiency, that resolve or are adequately controlled with physiologic hormone replacement (corticosteroids, thyroid hormones) or glucose-controlling agents, respectively, may not require discontinuation after mandatory discussion with and approval from the study medical monitor/designee.
- Grade 3 or 4 hypersensitivity reaction or infusion reaction. Please refer to Section 5.9 on Treatment of Related Infusion Reactions
- Any event that leads to delay in dosing lasting > 8 weeks (2 or more consecutive IV drug cycles missed) from the previous dose requires discontinuation, with the following exceptions:
 - Dosing delays to allow for prolonged steroid tapers to manage drug-related AEs are allowed.
 - Dosing delays lasting > 8 weeks (2 or more consecutive IV drug cycles missed) from the previous dose that occur for non-drug-related reasons may be allowed if approved by the study medical monitor/designee.

Prior to re-initiating treatment in a participant with a dosing delay lasting > 8 weeks (2 or more consecutive IV drug cycles missed), the study medical monitor must be consulted. Tumor assessments should continue as per protocol even if dosing is delayed. Periodic study visits to assess safety and laboratory studies should also continue every 6 weeks or more frequently if clinically indicated during such dosing delays.

• Any AE, laboratory abnormality, or intercurrent illness that, in the judgment of the investigator, presents a substantial clinical risk to the participant with continued IV study drug dosing.

Please refer to Appendix 8: AE Criteria for Delay, Resume and Discontinue of Nivolumab.

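### Protocol rules for held IV study drug conflict: Section 5.6 and Section 5.6.4.2 allow different exceptions to the 8-week limit, and Sections 5.6.1.2 and 5.6.4.2 set different minimum monitoring intervals

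*Protocol*

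**What the plan says.** **The 8-week limit.** Protocol Section 5.6 (Dose Modification Criteria) states that an IV dosing delay of more than 8 weeks, glossed as two or more consecutive cycles, "requires discontinuation except if approved by the study medical monitor/designee". It places no restriction on the reason for the delay.

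Section 5.6.2.2 counts the 8 weeks from the last dose, adds the same gloss, and says "the subject must be permanently discontinued from study therapy, except as specified in Section 5.6.4.2".

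Section 5.6.4.2 counts from the previous dose and lists two exceptions. Delays for prolonged steroid tapers to manage drug-related adverse events are allowed, and approval is not named as a condition. The other exception is for delays beyond 8 weeks "that occur for non-drug-related reasons may be allowed if approved by the study medical monitor/designee". The medical monitor must also be consulted before any restart after more than 8 weeks.

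**Monitoring during a hold.** Section 5.6.1.2 says: "Participants who require dose hold should be re-evaluated weekly or more frequently if clinically indicated and resume dosing during the next scheduled dosing window", that window being Day 1 ± 3 days. Section 5.6.4.2, directly after its sentences on delays beyond 8 weeks, says of periodic safety visits and blood work that "laboratory studies should also continue every 6 weeks or more frequently if clinically indicated during such dosing delays".

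**The underlying schedule.** IV drug is given "via a 30-minute IV infusion on Day 1 of every 28-day cycle, starting on Cycle 2" (Section 5.5.2). Patients attend "on Day 1 and Day 15 of Cycles 1 and 2, and on Day 1 of every cycle thereafter" (Section 3.1.3; Table 5 agrees).

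**The concern.** A site with a patient whose IV hold is approaching 8 weeks needs two answers: may IV drug continue, and how often must the patient be seen? The Protocol gives more than one answer to each.

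On the first, whether a patient stays on nivolumab or IV placebo can turn on which section the site consulted. On the second, the lowest stated frequency applies to the longest delays, and it follows a rhythm that the visit schedule does not use.

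The matter bears on patient safety and on the meaning of reported data. The combination SAP summarises IV discontinuations with their primary reason (Section 4) and the number, reasons and length of IV delays (Section 7.1). If sites read the limit differently, those tables mix clinical events with differences in interpretation.

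**Working it through.** The plan gives no figure to reproduce here. The check sets the rules side by side and then applies calendar arithmetic.

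**Step 1. Exceptions to the limit, for an IV delay beyond 8 weeks**

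| Reason for delay | Section 5.6 | Section 5.6.4.2 (to which 5.6.2.2 defers) |
|---|---|---|
| Drug-related, prolonged steroid taper | May continue if approved | Allowed; approval not named; consultation before restart |
| Not drug-related | May continue if approved | May continue if approved; consultation before restart |
| Drug-related, no steroid taper | May continue if approved | No exception: permanent discontinuation |

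The third row is a direct contradiction. The first row differs in the approval requirement. The second row agrees on approval.

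**Step 2. Minimum monitoring**

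Inputs: weekly (Section 5.6.1.2), every 6 weeks = 42 days (Section 5.6.4.2), scheduled visits every 28 days (Section 3.1.3, Table 5).

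- Two missed infusions give a nominal gap between doses of 3 × 28 = 84 days.
- Minimum checks if each interval is applied across the whole gap, counting day 84: weekly 84/7 = 12; 28-day visits 84/28 = 3; six-weekly 84/42 = 2.
- Ratio of the two stated minimums: 42/7 = 6.
- Fit to the visit cycle: day 42 lies 14 days from the nearest Day 1 (day 28 or day 56). The 42-day and 28-day grids coincide only every 84 days, their least common multiple.

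The six-weekly clause most naturally refers to delays beyond 8 weeks, so the overlap is certain only for those. Section 5.6.1.2 states no end point and so still covers them.

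**Step 3. Day count against cycle count (minor)**

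Inputs: 28-day cycle, window ± 3 days, limit 8 × 7 = 56 days.

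- One infusion missed: nominal restart 2 × 28 = 56 days after the last dose, which is not more than 8 weeks. With the restart window the range is 53 to 59 days, or 50 to 62 if the last dose also used its window.
- A restart on days 57 to 59 is therefore more than 8 weeks from the last dose although only one cycle was missed.
- Two infusions missed: nominal restart 84 days after the last dose, which is 84 − 28 = 56 days after the missed due date. Section 5.6 gives no starting point for its delay. Counted from the due date, two missed cycles are exactly 8 weeks and not more.

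The two descriptions of the limit are therefore close but not equivalent.

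**The case against.** **Section 5.6 is introductory.** It points to Sections 5.6.1 to 5.6.4 for detail, and 5.6.2.2 defers expressly to 5.6.4.2, so a careful reader could treat 5.6.4.2 as governing. This weakens the contradiction but does not remove it: the introductory text grants a permission that the detailed text lacks, and no order of precedence is stated. Appendix 8 has no 8-week rule to settle it.

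**The monitoring clauses are compatible in practice.** Both are recommendations, and both allow more frequent checks, so weekly review meets both. Patients still taking oral drug keep their 28-day visits with haematology and chemistry, and Section 5.6.4.2 requires checks every 3 days for certain hepatic elevations. All of this stands. What remains is that the stated minimums differ.

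**The gloss settles the trigger.** All three statements of the limit equate it with two or more missed cycles, and a patient restarting on days 57 to 59 has missed one. Discontinuation would follow only if the day count overrode the gloss. This stands, and it makes Step 3 a wording point only.

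**Practical value.** Randomization was expected to close in the third quarter of 2020 (Protocol Section 9.2.2), treatment is capped at 24 months after combination dosing starts, and the combination SAP (Section 7.1) expects all patients to be off treatment at the visit cut-off. The remaining value may lie mainly in reporting.

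**Conclusion.** Two inconsistencies hold on the text. A drug-related IV delay beyond 8 weeks without a steroid taper is approvable under Section 5.6 and ends IV treatment under Section 5.6.4.2. The minimum monitoring frequency during delays beyond 8 weeks is weekly in one section and six-weekly in another: 12 against 2 checks over 84 days, assuming each interval is applied across the whole gap. The mismatch between days and missed cycles is minor. Sample size, power and alpha are unaffected.

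A reader might infer more, and the documents do not support it:

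- *That Section 5.6.2.2 also ends oral drug.* It refers to study therapy without naming IV drug, but the section is headed for nivolumab/IV placebo and counts IV cycles, and Section 5.6.4 lets each agent be stopped independently.
- *That the 8-week rule would remove a large share of patients.* With visit dates spread evenly over the seven allowed days, 3/7 = 43% of single-miss restarts would fall after day 56. That is a share crossing a date under an assumed spread, not a discontinuation rate.
- *That nivolumab exposure in Arm A is reduced.* The documents do not say how many patients miss exactly one infusion or how sites apply the rule.
- *That the longest holds mark the most serious immune toxicity.* Many of the most serious events require permanent discontinuation, not a hold, and delays beyond 8 weeks expressly include non-drug-related ones.

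**What to change.** Reconcile Protocol Sections 5.6, 5.6.1.2, 5.6.2.2 and 5.6.4.2 with Table 5 so that they state:

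1. one set of exceptions to the 8-week IV limit, with one approval requirement;
2. one minimum monitoring frequency during an IV hold, including holds beyond 8 weeks;
3. a limit whose day count and missed-cycle count agree once the ± 3-day window is taken into account.

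Which exceptions, interval and limit to adopt is for the sponsor's medical team. The statistical requirement is only that there be one rule.

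If dosing has ended, document which reading was applied when the IV delays and discontinuations in Sections 4 and 7.1 of the combination SAP are reported.

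The cost is a few sentences of protocol wording and a clarification to sites, or a short note in the report. No analysis changes.

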5.7 Management Algorithms for Oral Study Drug

5.7.1 Management of Anemia

If anemia CTCAE Grade ≥ 3 occurs and persists for > 14 days, or a dependence upon blood transfusions occurs, then weekly complete blood counts are recommended until resolution of the anemia to \leq Grade 1. If after 42 days of treatment interruption anemia has not improved to Grade ≤ 1 , a referral to a hematologist and analysis of the bone marrow according to institutional standard practice is recommended.

Refer to Sections 8.3 and 8.7 of the protocol for additional information regarding classification and reporting of MDS or AML as an AESI.

5.7.2 Management of New or Worsening Pulmonary Symptoms Suggestive of Pneumonitis

If new or worsening unexplained pulmonary symptoms suggestive of pneumonitis (including, but not limited to, dyspnea) occur, or a deterioration of pulmonary function is observed, and/or radiologic abnormality is detected in the lungs, and this occurs in the absence of any clear diagnosis, a diagnostic workup (including high resolution CT scan) in consultation with a pulmonologist should be performed in order to rule out pneumonitis. During this time, treatment with oral study drug may be interrupted or continued per investigator discretion. The contribution of IV study drug should also be assessed independently.

Following investigation, if pneumonitis is not confirmed, treatment with oral study drug may be resumed/continued as deemed appropriate by the investigator and in accordance with the study protocol directions for management of AEs. All confirmed events of pneumonitis should be treated as appropriate per medical judgement and institutional guidelines. If the event resolves and retreatment with oral study drug is being considered, please consult the study medical monitor. Re-treatment with oral study drug may be resumed at the current or a reduced dose, if appropriate.

Refer to Sections 8.3 and 8.7 of the protocol for additional information regarding classification and reporting of pneumonitis (and similar events) as an AESI.

5.8 Management Algorithms for Immuno-Oncology Agents

Immuno-oncology (I-O) agents are associated with AEs that can differ in severity and duration than AEs caused by other therapeutic classes. Nivolumab is considered an I-O agent in this protocol. Early recognition and management of AEs associated with I-O agents may

mitigate severe toxicity. Management Algorithms have been developed to assist investigators in assessing and managing the following groups of AEs:

- Gastrointestinal
- Renal
- Pulmonary
- Hepatic
- Endocrinopathy
- Skin
- Neurological
- Myocarditis

The above algorithms are found in Appendix 7 of this protocol.

5.9 Treatment of Infusion-related Reactions

Since nivolumab contains only human immunoglobulin protein sequences, they are unlikely to be immunogenic and induce infusion or hypersensitivity reactions. However, if such a reaction were to occur, it might manifest with fever, chills, rigors, headache, rash, pruritus, arthralgias, hypotension, hypertension, bronchospasm, or other allergic-like reactions. All Grade 3 or 4 infusion reactions should be reported within 24 hours to the study medical monitor and reported as an SAE if it meets the criteria. Infusion reactions should be graded according to NCI CTCAE (v5.0) guidelines.

Treatment recommendations are provided below and may be modified based on local treatment standards and guidelines, as appropriate:

For Grade 1 symptoms: (mild reaction; infusion interruption not indicated; intervention not indicated):

• Remain at bedside and monitor participant until recovery from symptoms. The following prophylactic premedications are recommended for future infusions: diphenhydramine 50 mg (or equivalent) and/or acetaminophen/paracetamol 325 to 1000 mg at least 30 minutes before additional IV study drug administrations.

For Grade 2 symptoms: (moderate reaction required therapy or infusion interruption but responds promptly to symptomatic treatment (eg, antihistamines, non-steroidal anti-inflammatory drugs, narcotics, corticosteroids, bronchodilators, IV fluids); prophylactic medications indicated for ≤ 24 hours):

• Stop the study treatment infusion, begin an IV infusion of normal saline, and treat the participant with diphenhydramine 50 mg IV (or equivalent) and/or

acetaminophen/paracetamol 325 to 1000 mg; remain at bedside and monitor participant until resolution of symptoms. Corticosteroid and/or bronchodilator therapy may also be administered as appropriate. If the infusion is interrupted, then restart the infusion at 50% of the original infusion rate when symptoms resolve; if no further complications ensue after 30 minutes, the rate may be increased to 100% of the original infusion rate. Monitor participant closely. If symptoms recur, then no further study treatment will be administered at that visit.

• For future infusions, the following prophylactic premedications are recommended: diphenhydramine 50 mg (or equivalent) and/or acetaminophen/paracetamol 325 to 1000 mg should be administered at least 30 minutes before IV study drug infusion. If necessary, corticosteroids (up to 25 mg of hydrocortisone or equivalent) may be used

For Grade 3 or 4 symptoms: (severe reaction, Grade 3: prolonged [ie, not rapidly responsive to symptomatic medication and/or brief interruption of infusion]; recurrence of symptoms following initial improvement; hospitalization indicated for other clinical sequelae (eg, renal impairment, pulmonary infiltrates). Grade 4: Life-threatening; pressor or ventilatory support indicated):

• Immediately discontinue infusion of study drug. Begin an IV infusion of normal saline and treat the participant as follows: Recommend bronchodilators, epinephrine 0.2 to 1 mg of a 1:1000 solution for subcutaneous administration or 0.1 to 0.25 mg of a 1:10,000 solution injected slowly for IV administration, and/or diphenhydramine 50 mg IV with methylprednisolone 100 mg IV (or equivalent), as needed. Participant should be monitored until the investigator is comfortable that the symptoms will not recur. Study drug will be permanently discontinued. Investigators should follow their institutional guidelines for the treatment of anaphylaxis. Remain at bedside and monitor participant until recovery of the symptoms.

In case of late-occurring hypersensitivity symptoms (eg, appearance of a localized or generalized pruritus within 1 week after treatment), symptomatic treatment may be given (eg, oral antihistamine or corticosteroids).

